2.0 Background

2.1 Significance of Research Question/Purpose:

Since appearing in Wuhan, China in December 2019, the severe acute respiratory syndrome coronavirus 2 (SARS-CoV-2) has caused disease (COVID-19) in over 155,000 people with over 5,900 deaths to date across 100 countries.¹⁻³ The mortality is estimated at 3.7%,⁴ with infectivity (R_0) estimated at 2.24 to 3.585,⁵ with morbidity and mortality disproportionately affecting the elderly.⁶ Most severely affected patients are admitted for respiratory support and die of respiratory failure.^{7,8} At present there is no current specific treatment for patients with COVID-19.⁹ The novel coronavirus is closely related to the severe acute respiratory syndrome coronavirus (SARS-CoV) which caused an outbreak of disease (SARS) in 2003; this may inform the development of novel treatments.^{9,10} Attempts to develop vaccines since SARS or middle eastern respiratory virus (MERS) have been unsuccessful, will take time, and may or may not be effective for this or future coronavirus pandemics.¹¹ Extensive efforts to date, therefore, have been appropriately focused on screening, identification, and containment with collaboration and coordination within and between governments to combat its spread.¹²

Due to the nature of coronavirus cellular binding, there exist several promising novel pharmacotherapeutic strategies that differentiate this virus from seasonal or pandemic influenza. Similar to the 2002-2003 SARS-CoV, the SARS-CoV-2 virus binds the spike protein of angiotensin-converting enzyme 2 (ACE2), a critical component of the renin-angiotensin-aldosterone (RAAS) system, in order to enter the cell.¹³ (Figure 1 – red arrow on right)

Multiple proposed interventions to combat SARS-CoV-2 under development focus on this pathway with the goal of blocking viral entry into cells, and include anti-viral agents,¹⁴ anti-malarial medications,¹⁵ vaccines,¹⁶ and viral protein inhibitors.⁹ While these therapies are promising, immediate use of these interventions are not feasible. In many cases, drugs are still under development and lack a clinical indication, with limited safety and efficacy data in humans to date. These factors will necessarily lead to delays in drug development. Given the rapid spread of SARS-CoV-2, patients would greatly benefit from interventions

[figure not shown]

Fig. 1 Potential approaches to address ACE2-mediated COVID-19 following SARS-CoV-2 infection. The finding that SARS-CoV-2 and SARS-CoV use the ACE2 receptor for cell entry has important implications for understanding SARS-CoV-2 transmissibility and pathogenesis. SARS-CoV and likely SARS-CoV-2 lead to downregulation of the ACE2 receptor, but not ACE, through binding of the spike protein with ACE2. This leads to viral entry and replication, as well as severe lung injury. Potential therapeutic approaches include a SARS-CoV-2 spike protein-based vaccine; a transmembrane protease serine 2 (TMPRSS2) inhibitor to block the priming of the spike protein; blocking the surface ACE2 receptor by using anti-ACE2 antibody or peptides; and a soluble form of ACE2 which should slow viral entry into cells through competitively binding with SARS-CoV-2 and hence decrease viral spread as well as protecting the lung from injury through its unique enzymatic function. MasR—mitochondrial assembly receptor, AT1R—Ang II type 1 receptor

Figure 1: Mechanisms of Action of SARS-CoV-2 interaction with the Renin Aldosterone Angiotensin System and possible therapeutic options proposed by Zhang et al.⁹

with a well-established safety profile readily available for immediate clinical trial testing and rapid knowledge translation if efficacious.

2.2 Rationale and Scientific Hypothesis:

Renin-aldosterone blockade has been proposed as a potential treatment for COVID-19.¹⁷⁻¹⁹ This hypothesis was originally published by Sun et al¹⁹ on February 16, 2020 (manuscript published in Chinese) and in the British Medical Journal on February 4, 2020.¹⁸ This hypothesis was reinforced in Drug Development Research on March 4, 2020.¹⁷ To the best of our knowledge, our study is the first investigating this hypothesis.

As opposed to ongoing clinical trials targeting viral binding and entry, the proposed clinical trial proposes to mitigate the respiratory consequences of SARS-CoV-2, thereby reducing morbidity and mortality. As illustrated in Figure 1, SARS-CoV-2 binds to angiotensin converting enzyme 2 (ACE2), similar to 2002-2003 SARS-CoV. Molecular simulation has shown SARS-CoV-2 has a higher affinity for ACE2 compared with SARS-CoV.²⁰

Healthy State:

In states of health, ACE2 converts Angiotensin 2 (ATII) into lung-protective angiotensin (AT) 1-7 and 1-9, thus preventing unopposed ATII activation of AT1R. Unopposed AT1R activation triggers a downstream pro-inflammatory cascade, characterized by increased lung permeability, acute lung injury (ALI), acute respiratory distress syndrome (ARDS), and death (**Figure 2**).^{4,18} AT1R activation also leads to type II pneumocyte apoptosis, a common feature of ARDS.^{12,13} Therefore, under usual conditions of health, ACE2 prevents lung injury.

Infection with SARS-CoV-2:

Impaired ACE2 activity due to binding with SARS-CoV-2 results in excessive ATII allowing unopposed binding of AT1R without generation of lung-protective AT1-7 and AT1-9 (**Figure 2**).^{21,22} An ongoing clinical trial is attempting to exploit this mechanism by treating 24 patients with recombinant human ACE2

[figure not shown]

Figure 2: Proposed mechanism of Losartan in disrupting the pro-inflammatory and injurious pathway caused by over stimulation of AT1R in the setting of SARS-CoV-2 infection. ACE1-Angiotensin converting enzyme 1, AT1R-Angiotensin I receptor, ACE2-Angiotensin converting enzyme 2, AT-1-7-Angiotensin 1-7.

(rhACE2) infusions.²³ Infusions of ACE2 have previously been shown to result in decreased AT2 and increased AT1-7.²⁴ Unfortunately, protein recombinant human infusions are costly and scaling production will take significant time.

Given this, we propose to leverage a readily available angiotensin receptor blocker (ARB) with an excellent safety profile, losartan, to mitigate this pathway with the aim of

decreasing ALI/ARDS. While ACE inhibitors (ACEi) could also be considered for trial, ACEi are frequently associated with cough which could exacerbate the spread of the disease. In 2-8 week studies, losartan had 17% and 27% rates of cough vs 69% and 62% (see package insert). Furthermore, ACE inhibitors can induce expression of ACE2 secondary to low local angiotensin II levels, potentially increasing viral uptake.

Preclinical Supporting Data:

SARS-CoV specific preclinical work:

In 2003, ACE2 was identified as the binding protein for SARS-CoV.²⁵ This was validated in 2005 by Kuba et al. This same study identified that SARS-CoV injury worsens acute lung injury and can be attenuated by Renin-Angiotensin (RAS) pathway inhibition.²² Kuba first identified that ACE2 knockout mice had significantly lower viral loads in the lung following infection, whereas wildtype (wt) mice had very high viral loads.²² Additionally, wt mice had significantly higher lung injury scores following SARS-CoV infection.²² SARS-CoV infection results in downregulation of its binding protein ACE2 (ACE2 has been shown to be lung protective in its action of converting AT2 -> AT1-7).²² This finding that SARS-CoV results in downregulation of ACE2 has been validated in subsequent studies.²⁶ Kuba et al, then showed that treatment with Losartan 15 mg/kg attenuated lung injury (**Figure 3B**) and the development of pulmonary edema (**Figure 3C**) in mice infected with SARS-CoV Spike-FC.²² For this study 2.5-3 month old mice received SARS-CoV Spike-FC. 30 minutes later they received HCL to expedite lung injury. Mice were then randomized to Losartan vs vehicle. 1 and 2 hours later SARS-CoV Spike-FC. Mice then received 3 hours of mechanical ventilation and were sacrificed. (**Figures 3B and C**).²²

[figure not shown]

Figure 3: (A) Mechanism of SARS-CoV infection. (green diamond) treated with Angiotensin II receptor inhibitor (Losartan) (purple triangle) or Angiotensin II receptor inhibitor (Mutant Losartan) (green circle) and (red square) vehicle. (B) ACE2 knockout (KO) mice treated with recombinant ACE2 (rhuACE2) (red square) or vehicle (red diamond) and (blue square) or mutant rhuACE2 (blue triangle) and (green square) vehicle. (C) ACE2 knockout (KO) mice treated with recombinant ACE2 (rhuACE2) (red square) or vehicle (red diamond) and (blue square) or mutant rhuACE2 (blue triangle) and (green square) vehicle. Figures from Kuba et al, *Nature*, 2005

In 2005, Imai et al showed that loss of ACE2 leads to significantly worse

[figure not shown]

Figure 4: (A) ACE2 knockout (KO) mice treated with recombinant ACE2 (rhuACE2) versus vehicle or mutant rhuACE2 showed reduced lung injury (B) ACE2 knockout (KO) mice treated with recombinant ACE2 (rhuACE2) versus vehicle or mutant rhuACE2 showed reduced wet/dry ratio. Figures from Imai et al, *Nature*, 2005

MEDICAL PROTOCOL (HRP-590)

SHORT PROTOCOL TITLE: Randomized control trial of losartan for outpatients with COVID-19

VERSION DATE: 5APR2020

oxygenation, massive lung edema, and inflammatory cell infiltration in mice compared to wildtype mice in response to acid aspiration.²¹ They then performed a rescue experiment and showed that supplementation with rhACE2 rescued infected mice (**Figure 4A, B: green circles vs purple triangle and dark pink diamond**).²¹

[figure not shown]

Figure 5: (A) ACE2 knockout (KO) mice treated with acid-induced ARDS treated with AT2R inhibition (pink triangle), AT1R inhibition (light purple triangle), or vehicle (purple square). *Figures from Imai et al, Nature, 2005*

Yang et al, Sci Rep, 2014).^{27,28} Yiwu et al found that Losartan at doses equivalent to those used for clinical treatment of humans were associated with increased survival, decreased lung edema and lung injury scores, and decreased IL-6 for mice infected with H5N1 (**Figure 6 A-E**) (Yiwu et al, Sci China Life Sci, 2015).²⁹

Yang et al infected 4-week-old mice with either influenza H7N9 or placebo.²⁸ Mice were given Losartan 30 minutes prior to viral infection. They identified that inhibition of AT1R attenuates

H7N9 lung injury and was associated with lower wet-dry ratios and lower infiltrative cell counts (Yang et al, Sci Rep, 2014).²⁸

[figure not shown]

Figure 6: (A) Study Design (B) Mice infected with H5N1 had improved survival when treated with losartan versus control (C) Mice infected with H5N1 had less pulmonary edema when treated with losartan versus control (D) Mice infected with H5N1 had decreased pulmonary inflammation when treated with losartan versus control (E) Mice infected with H5N1 had reduced lung injury score when treated with losartan versus control (F) Mice infected with H5N1 had increased ACE2 (lung protective) and reduced ACE1 (lung deleterious) when treated with losartan versus control. *Figures from Yiwu et al, Sci China Life Sci, 2015*

Imai et al. demonstrated inhibition of AT1R via losartan reduced lung injury (**Figure 5, light purple triangle**) compared with vehicle (**Figure 5, purple square**). This pathway was specific to inhibition of AT1R as, inhibition of AT2R did not reduce lung injury (**Figure 5, pink triangles**) For this study ACE2 knockout (KO) mice were given AT1R (losartan) or AT2R 30 minutes prior to acid-induced acute respiratory distress syndrome (ARDS).²¹

Preclinical supporting data for Renin-Angiotensin inhibition in other viral pneumonias that interact with ACE2:

[figure not shown]
Both influenza H7N9 and H5N1 have been implicated to cause lung injury through ACE2 with resultant upregulation of angiotensin-2 and AT1R induced lung injury (Zou et al., Nature Communications, 2014 and

2.3 Existing Literature:

There is no existing literature regarding the effect of losartan in COVID-19. **To that effect there is limited literature regarding the effectiveness of any treatments on COVID-19.** Data of relevance to are summarized in 2.1-2.3.

There is an urgency to identify effective and readily available treatments for patients with COVID-19. This proposed study will elucidate the role of losartan, this is based on strong physiologic and preclinical data as described in detail above.

There is a critical and dire need to identify and evaluate all possible methods to minimize the burden of COVID-19 on our society and healthcare system. At the current rate of growth (as of 3/13/2020) America is 1 week from widespread outbreak similar to Italy and Iran. Unfortunately, current community efforts are not sufficiently slowing down spread as our slope (see Figure below) is higher in the last few days than the rest of the world.

3.0 Study Endpoints/Events/Outcomes

3.1 *Primary Endpoint/Event/Outcomes:* The primary endpoint is the need for hospital admission at 15 days from randomization.

3.2 *Secondary Endpoint(s)/Event(s)/Outcome(s):*

- Subjective improvement in dyspnea as measured by the dyspnea PROMIS measures (survey attached) at day 0, 4 and 10
- Daily maximum temperature
- Number of emergency department or clinic presentations within 28 days
- Disease severity rating on the *7-point ordinal scale* [Time Frame: Day 7, 15, 28]
 - The *7-point ordinal scale* is an assessment of the clinical status at the first assessment of a given study day. The scale is as follows: 1) Death; 2) Hospitalized, on invasive mechanical ventilation or extracorporeal membrane oxygenation (ECMO); 3) Hospitalized, on non-invasive ventilation or high flow oxygen devices; 4) Hospitalized, requiring supplemental oxygen; 5) Hospitalized, not requiring supplemental oxygen; 6) Not hospitalized, limitation on activities; 7) Not hospitalized, no limitations on activities
- Change in viral load by oropharyngeal swab
- Ventilator free days, oxygen free days
- Need for hospital admission and oxygen therapy at 15 days

3.3 *Justification of the primary outcome:* This trial seeks to mitigate lung injury from COVID-19 rather than treating the viral infection. Most patients present to the hospital secondary to dyspnea and pneumonia, and the primary mechanism of death is via respiratory failure progressing to multi-system organ failure. Prevention of acute lung injury with an angiotensin receptor blocker such as losartan may reduce the development of the primary need for hospitalization. **This is a clinically relevant outcome not only to patients, but also to the healthcare system due to overwhelming surge of patients straining hospital resources which not only puts patients with COVID-19 at risk, but also those admitted to the hospital for other reasons.** It is important to emphasize the critical need for research studies that identify effective treatments that mitigate the progression of disease requiring hospitalization. **To provide a specific example**, Minneapolis has a metropolitan population of 3.4 million residents with approximately 5000 inpatient hospital beds and 500 ICU beds. If only 1% of the Minneapolis population developed symptomatic COVID-19 that would equate to 34,000 patients. Studies support a 13-15% hospitalization rate both in the US (as of the time of this writing New York state has 421 cases, 50 hospitalized, 13 in ICU) and internationally³⁰ which would constitute 4420 – 5100 beds, nearly the entire metropolitan hospital capacity.

3.4 *Justification of the secondary outcomes:* Validated study instruments to assess dyspnea and physical function will assess patient-centered outcomes and strengthen the biologic plausibility of the intervention. A decrease in inflammation through the reduction of pulmonary edema may be observed as a change in fever. The study drug could affect the number of presentations requiring evaluation but not result in hospital admission. The 7-point ordinal scale described is used by other ongoing COVID-19 clinical trials and will allow harmonization of the trial results.

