 - Patient-reported comorbidities [hypertension (requiring or not requiring medication), diabetes mellitus (insulin or non-insulin dependent), coronary artery disease, myocardial infarction, congestive heart failure (with preserved or reduced ejection fraction, if known), pacemaker or AICD, asthma (with or without emergency department evaluation and / or hospital admission in the past year), chronic obstructive pulmonary disease, chronic bronchitis, chronic steroid use, history of transplant (with type),

MEDICAL PROTOCOL (HRP-590)

SHORT PROTOCOL TITLE: Randomized control trial of losartan for outpatients with COVID-19

VERSION DATE:5APR2020

arrhythmias including atrial fibrillation, dialysis, angina, pulmonary hypertension and obstructive sleep apnea, renal disease, liver disease, tobacco and alcohol use history, recent pregnancy or breastfeeding history, height and weight]

- Self-reported home medications [antihypertensives, insulin, non-insulin diabetes medications, corticosteroids (inhaled or systemic), other immunosuppressants hydroxychloroquine, other COVID-directed treatments] or home oxygen use
- Use of outpatient COVID-directed treatments (such as hydroxychloroquine, Tylenol, ibuprofen, azithromycin, or others)
- PROMIS Pool v1.0 Dyspnea Characteristics Survey (5 question Likert scale survey) (attached) with date/time of administration
- Short form 12 (SF-12) health survey (attached) with date/time of administration
- Oropharyngeal swab every third day (performed, yes or no)
- Lowest home blood pressure daily
- Highest home temperature daily
- Medication adherence
- Hospital admission (with date, if applicable)
 - a. If admitted: initial vital signs, initial and highest method of respiratory support (oxygen by nasal cannula, facemask, high flow nasal cannula, CPAP, BIPAP, endotracheal intubation, ECMO), initial and worst measures of organ failure (SOFA score), and initial and worst markers of cardiac injury (troponin, BNP/pro-BNP. CXR or CT chest results will be recorded. If patients are admitted to non-MHealth or HCMC hospitals, we will contact the patient to obtain permission to request data from their hospitalization.
- Date of death (if applicable)
- Study withdrawal, with date and time (if applicable)

- Final outcome follow-ups will be determined through a combination of patient report, electronic medical record review, and review of the social security death index (SSDI).

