4.3 *Investigational new drug.* The study will undergo pre-IND review with the Food and Drug Administration to determine the need for an investigational new drug assessment, and will be assigned an IND number if required.

4.4 *Timing of the intervention:* Treatment will continue for 10 days or attainment of the primary outcome (hospital admission).

4.5 *Duration of study participation:* The final follow-up will occur at 90 days after randomization to determine episodes of delayed hospitalization. Data analysis is expected to be completed within 1 year of enrollment of the final patient.

4.6 *Drug Handling, blinding, and randomization:*

Fairview Investigational Drug Services (IDS), part of M Health Fairview will oversee the preparation of treatment drug and placebo. Identical pills (#20) will be placed in identical

MEDICAL PROTOCOL (HRP-590)

SHORT PROTOCOL TITLE: Randomized control trial of losartan for outpatients with COVID-19

VERSION DATE:5APR2020

bottles with a deidentified study number coded by site and patient number (e.g. 01-001, 02-001, etc.). A site-specific randomization schema will be created (each site will undergo permuted block randomization with random block sizes stratified by site and age). Given significant differences in outcome by age, patients will be randomized by age strata (≥ 50 , < 50). Randomization allocation will be 1:1. IDS will not be blinded to patient randomization. All other members of the study, the participants, and the clinical care team will be blinded to treatment allocation.

4.7 *Provision of study drug to patients*: Following randomization, a courier service will ship drugs to study participants within 24 hours of randomization. Each dispensing will contain 20 capsules, enough to complete the 10-day therapy

4.8 *Study unblinding*: MHealth Fairview, East bank Inpatient Pharmacy UMMC campus, will hold the blind for all subjects on study. In the event of an emergency and unblinding is necessary, study staff can contact [contact], option 1, then option 2. This information is included on each label.

4.9 *Biosafety*: N/A. The intervention is not a biohazard.

4.10 *Stem Cells*: N/A

4.11 *Fetal Tissue*: N/A

4.12 *Use of radiation*: N/A

4.13 *Use of Center for Magnetic Resonance Research*: N/A

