15.0 Statistical Considerations

- 15.1 *Data Analysis Plan:* All analysis will focus on comparisons between the treatment and control groups. Demographics and other baseline clinical characteristics will be summarized using descriptive statistics. Descriptive statistics will be presented by treatment group using mean, standard deviation, median, and interquartile range (IQR) for continuous variables and frequencies and percentages for categorical variables. The primary outcome, hospitalization at day 15, will be summarized by group using the sample proportion with 95% asymptotic confidence intervals. Treatment groups will be compared using the Chi-square test and the treatment

effect will be summarized by the absolute difference in the hospitalization rate between groups. Secondary endpoints will be summarized by the mean and standard deviation and compared using the two-sample unequal variance t-test, potentially after appropriate data transformations to assure that assumptions of the t-test are met. Time-to-event endpoints will be summarized by Kaplan-Meier curves and compared using Cox proportional hazards regression. For all endpoints, we will complete secondary analyses comparing for important baseline variables that are unequally distributed between treatment groups. Preplanned subgroup analyses are planned by age (dichotomized at 50 and by decade), history of hypertension, sex, and smoking history, timing of randomization from symptom onset, and respiratory support needed at the time of randomization. In addition, we will perform a preplanned pooled analysis with a planned national outpatient trial of losartan versus placebo targeting the same patient population with harmonized assessments and outcomes.

15.2 *Power Analysis:* Previously published literature from China suggest a 15% hospitalization rate for patients infected with coronavirus.^{7,30} To detect a difference in hospital admission rate of 15% in control vs. 7% in the intervention group, with alpha of 0.05 and 80% power using a two-sided test, we will need 264 patients in each group. We will enroll a total of 290 patients in each group (total sample size of 580) to account for the possibility of 10% loss-to-follow-up.

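### The primary endpoint counts hospital admission only, and no rule says how a death before admission is scored

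*Combined protocol and SAP*

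**What the plan says.** The definition is consistent throughout the combined protocol and SAP. Sections 1.2 and 1.3 frame the purpose and hypothesis as the rate of hospitalization. Section 3.1 reads: "The primary endpoint is the need for hospital admission at 15 days from randomization". Section 4.4 equates the primary outcome with hospital admission. Section 15.1 states: "The primary outcome, hospitalization at day 15, will be summarized by group using the sample proportion with 95% asymptotic confidence intervals", and then: "Treatment groups will be compared using the Chi-square test". Section 15.2 sizes the trial on the same quantity: "To detect a difference in hospital admission rate of 15% in control vs. 7% in the intervention group".

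Death appears elsewhere, but never in the primary analysis:

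- Section 3.2 places it at the bad end of the secondary ordinal scale, assessed at days 7, 15 and 28: "1) Death; 2) Hospitalized, on invasive mechanical ventilation".
- Section 1.6 collects the date of death and plans a death index review.
- Sections 18.2 and 18.3 send deaths and hospitalizations to the DSMB as they occur.

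Section 12.1 applies intention to treat to withdrawn participants. It does not mention deaths.

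**The concern.** Death before admission prevents the primary event from happening. In a comparison of admitted with not admitted, such a participant falls in the not-admitted group, so the worst outcome is scored with the best. The misclassification always favours the arm in which the death occurs.

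The trial's setting makes the case possible. Participants are outpatients followed mainly by telephone. Section 3.3 expects COVID-19 admissions to take up almost all local beds. Section 13.1 lists symptomatic hypotension and angioedema among the most severe risks of losartan. Under section 5.4, non-response is simply documented, so a death at home could at first look like loss to follow-up. Without a written rule, the classification would be settled after the deaths are known.

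**Working it through.** **Inputs.** 15% vs 7%, two-sided alpha 0.05, 80% power, 264 per group, 290 enrolled per group, 10% loss (section 15.2); 1:1 allocation (section 4.6). The rate of death without admission, q, is not in the documents. I assume 0.25% to 1% and also show 2% for power.

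**1. The plan's own figure.** With p̄ = 0.11, the usual two-proportion formula is n₀ = [1.96·√(2p̄(1−p̄)) + 0.842·√(0.15·0.85 + 0.07·0.93)]² / 0.08² = 238.9. With the continuity correction, n = (n₀/4)·[1 + √(1 + 4/(n₀·0.08))]² = 263.4, which rounds up to 264. The plan's figure is reproduced for hospitalization alone. Enrolment follows as 264 × 1.1 = 290.4. After 10% loss, 290 × 0.9 = 261 per arm remain.

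**2. Weight of one death.** 1/261 = 0.38 percentage points, against a planned difference of 8. The assumed q gives 261 × 0.0025 = 0.7 to 261 × 0.01 = 2.6 such deaths per arm.

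**3. Effect on the test.** For equal arms, the uncorrected statistic is X² = (p₁−p₂)² / [2p̄(1−p̄)/n]. For 39 vs 23 of 261, p₁−p₂ = 0.0613 and p̄ = 62/522 = 0.1188, so X² = 4.69 and p = 0.030. The other cases follow in the same way:

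| Admissions, placebo vs losartan | Deaths before admission | Events if deaths count | p, admission only | p, deaths counted |
|---|---|---|---|---|
| 39 vs 23 | 2 on losartan | 39 vs 25 | 0.030 | 0.062 |
| 39 vs 23 | 2 in each arm | 41 vs 25 | 0.030 | 0.035 |
| 39 vs 23 | 2 on placebo | 41 vs 23 | 0.030 | 0.016 |
| 39 vs 18 (planned effect) | 2 on losartan | 39 vs 20 | 0.003 | 0.009 |
| 39 vs 18 (planned effect) | 7 on losartan | 39 vs 25 | 0.003 | 0.062 |

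The first three rows use 23/261 = 8.8% on losartan, a weaker effect than the planned 7%. With the continuity correction, which reproduces the plan's sample size, 39 vs 23 gives p=0.042, and a single losartan death (39 vs 24) gives p=0.060.

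**4. Power for a composite.** Add q to both arms and use power = Φ{[√n·0.08 − 1.96·√(2p̄(1−p̄))] / √(p₁(1−p₁) + p₂(1−p₂))} with n = 264 (uncorrected test). At q = 1%, this is Φ{(1.300 − 0.901)/0.456} = Φ(0.875) = 80.9%.

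| q in both arms | Power at 264 per group | n per group, continuity-corrected |
|---|---|---|
| 0 | 83.8% | 264 |
| 0.25% | 83.1% | 269 |
| 0.5% | 82.3% | 273 |
| 1% | 80.9% | 283 |
| 2% | 78.2% | 301 |

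If losartan instead lowers these deaths in the same proportion as admissions (7/15), the required n at q = 1% falls to 245.

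**The case against.** The strongest reply is that nothing in the plan says a death before admission is a success. Section 3.1 speaks of the need for admission, which could be read to cover someone who died before reaching a bed, or such deaths could be set to missing. That is correct as far as it goes: the non-event classification is the literal reading of a hospitalization proportion, not a stated rule. Neither alternative is written down, however. The broad reading leaves a judgement for later, and setting deaths to missing removes the worst outcomes from the comparison. All three routes need a sentence in the plan.

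The second reply concerns size, and it stands. Section 2.1 says most severely affected patients are admitted, and section 5.4 has participants telephoned every other day during treatment, so few deaths should escape admission. The loss of significance in the first table row needs a weaker-than-planned effect and deaths confined to losartan. Balanced deaths barely move the result, and deaths confined to placebo would make the current endpoint work against losartan.

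The third reply is that lethal harm is watched elsewhere: continuous reporting to the DSMB, formal safety looks from 5% to 50% of enrolment, and the ordinal scale. This limits the risk that harm would go unseen. It does not change how the final primary test is scored.

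**Conclusion.** The gap is real and should be closed, but its likely effect on the result is small. The primary endpoint omits death, and the plan does not classify death before admission. Read literally, such a death is a non-event.

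A reader might infer that the plan deliberately scores deaths as successes, or that losartan deaths would probably turn harm into apparent benefit. The documents support neither. There is no explicit scoring rule, no rate of unadmitted death is given, and at the planned effect it takes 7 deaths, all on losartan (7/261 = 2.7% of the arm), to lose significance in the uncorrected test. That is above the assumed maximum of 1%. Nor do the figures show that the trial must be enlarged: with an equal added rate of up to 1%, power at 264 evaluable per group stays above 80% on the uncorrected test. The sizes rest on the assumed q; the absence of a rule does not.

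**What to change.** Define the primary endpoint as hospital admission or death from any cause, at any time from randomization through day 15. At minimum, state in 15.1 that death before admission counts as an event. In either case, report admission alone and death alone as components.

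Align the wording in 1.2, 1.3, 3.1, 4.4, 15.1 and 15.2. In 4.4 only the phrase equating the primary outcome with admission needs attention; the treatment-duration rule is not at issue here. In 15.2, state what rate of death before admission the 15% and 7% are taken to include. Keep hospitalization alone as a supportive analysis, because 15.1 plans pooling with a national trial that uses harmonized outcomes.

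The cost is text only. Date of death, record review, telephone follow-up and the death index are already planned. The endpoint becomes slightly broader and may pick up a few deaths unrelated to COVID-19. If deaths before admission are equally common in both arms, power falls slightly, to about 81% at an assumed 1% (264 evaluable per group, uncorrected test). The planned sample size can stand if such deaths are rare.
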